11.7.5 Performance Analysis

A model/algorithm will be developed for the correlation between histological findings of NAFLD and OBT with or without MBT. It will be developed using either logistic regression or neural network or any other known methodology. Using a cut-point on the score a binary diagnosis of NASH (Yes/No) or NAFL (Yes/No) will be obtained. The minimal criterion for sufficient efficacy is an Area under the Receiver Operating Characteristics (ROC) Curve (AUC) ≥ 0.75 in this patient population. A potential clinical utility was designated for the algorithm/model output; where this algorithm could aid the clinician in ruling-in or out NASH or NAFL. This will be translated into finding a model prediction cut-point that provides a high sensitivity (true positive rate) and at least moderate specificity (true negative rate), which in turn achieves a high negative predictive value (NPV). High NPV is considered to be near 90% (i.e. 88%) thus sensitivity should be at least 90% and specificity should be at least 50%. Cross validation methods will be used to test algorithm stability.

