2. Discontinuance of study, if ≥ 2 patients on Octanoate/Methacetin develop the same CTCAE Grade 3 event or 1 patient develops a CTCAE Grade 4 or higher event due to one of the breath tests

[figure not shown]
Data Analysis / Statistics: An ROC analysis will be used to determine the optimal parameter and cut-offs for required performance measures sensitivity and specificity.

All efficacy analysis will include the point estimates of sensitivity, specificity, PPV and NPV with respective exact 95% confidence intervals. The respective Positive and Negative Predictive Values (PPV and NPV) will be presented as a function of possible NAFLD prevalence and will include the prevalence of the enrolled population.

This test will not replace biopsies to rule out other liver diseases such as autoimmune hepatitis, alcoholic hepatitis, alpha-1-antitrypsin deficiency, etc.

Exalenz Bioscience Ltd.	Last update on: May1, 2016
Study Title: Clinical Study of the BreathID [®] System to train the algorithm for the ¹³ C-Octanoate Breath Test with or without the ¹³ C-Methacetin Breath Test (OBT and MBT respectively) for correlation with histological findings of Non-Alcoholic Fatty Liver Disease (NAFLD)	Protocol No.: NASH-EX-1114
	Version: 1f
Document N^o: CSD00080	Page 15 of 61

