11.5 Sample Size estimation

It is estimated that a total of 200 subjects with a fresh and evaluable liver biopsy undergoing OBT and MBT of which at least 50 will be positive for NASH and at least 50 will be positive for NAFLD will enable the estimation of a conservative AUC of 0.75 with a half width of the 95% confidence interval of 0.1.

During the study the correlation between OBT with or without MBT and histological findings of NAFLD will be assessed periodically in order to see if there is any confounding factor(s) affecting the correlation. In the case that such a factor(s) is identified showing a significant difference in correlation, the study population may be increased up to 400 patients.

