11.7.6 Interim Analysis

This study is an open label study for training purposes. The data may be assessed prior to achieving the full sample size. This will be done specifically in order to assess the effect

Exalenz Bioscience Ltd.	Last update on: May1, 2016
Study Title: Clinical Study of the BreathID [®] System to train the algorithm for the ¹³ C-Octanoate Breath Test with or without the ¹³ C-Methacetin Breath Test (OBT and MBT respectively) for correlation with histological findings of Non-Alcoholic Fatty Liver Disease (NAFLD)	Protocol No.: NASH-EX-1114
	Version: 1f
Document N^o: CSD00080	Page 34 of 61

of confounding factors on the correlation between OBT with or without MBT and binary diagnosis of biopsy proven NASH or NAFL. If any confounding factor shows significantly different correlation than the rest of the population, the study population may be increased to up to 400 patients.

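### The AUC criterion of at least 0.75 is not tied to out-of-sample predictions, so it can be met on the data that trained the algorithm

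*Combined protocol and SAP*

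**What the plan says.** Section 11.7.5 gives the success rule as "The minimal criterion for sufficient efficacy is an Area under the Receiver Operating Characteristics (ROC) Curve (AUC") ≥ "0.75 in this patient population". The cut-point on the score should then give at least 90% sensitivity and at least 50% specificity. On how the model is built, the section says: "It will be developed using either logistic regression or neural network or any other known methodology". Its last sentence is the only mention of cross-validation in the document: "Cross validation methods will be used to test algorithm stability". No number of folds is given, and no consequence follows if the cross-validated result is poor.

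The synopsis adds "An ROC analysis will be used to determine the optimal parameter and cut-offs for required performance measures sensitivity and specificity" and "All efficacy analysis will include the point estimates of sensitivity, specificity, PPV and NPV with respective exact 95% confidence intervals".

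Section 11.5 plans 200 subjects, "of which at least 50 will be positive for NASH and at least 50 will be positive for NAFLD", with a possible increase to 400. Section 11.7.6 describes the study's purpose: "This study is an open label study for training purposes". Sections 8 and 11.1 state that the algorithm will be validated in a separate study. No split sample or optimism correction is planned within this one.

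**The concern.** The inputs, model family, tuning and cut-off are all chosen on the same patients who supply the AUC. An AUC computed on the data that trained the model overstates performance in new patients, and the overstatement grows with the number of candidate inputs and the flexibility of the model. The plan limits neither.

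The exact intervals for sensitivity and specificity have the same weakness. They assume a cut-off fixed before the data were seen, but here the cut-off comes from the same ROC curve. The intervals are therefore centred on optimistic values.

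At stake is a finding of sufficient efficacy for an algorithm that discriminates poorly in new patients, and a cut-off that under-delivers when it is carried into the validation study.

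**Working it through.** **1. The plan's own figure.** Section 11.5 states a 95% half-width of 0.1 at AUC 0.75. By Hanley-McNeil, with A = 0.75, a = A/(2−A) = 0.600 and b = 2A²/(1+A) = 0.643:

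SE² = [A(1−A) + (n₁−1)(a−A²) + (n₀−1)(b−A²)] / (n₁n₀)

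For 50 v 50: (0.1875 + 49×0.0375 + 49×0.0804)/2500 = 0.00239, so SE = 0.0488 and the half-width is 1.96 × 0.0488 = 0.096. The Obuchowski binormal formula gives 0.102, and Hanley-McNeil at 50 v 150 gives 0.085. The stated 0.1 reproduces, but these formulas treat the score as fixed in advance. They make no allowance for fitting or selection.

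**2. Candidate inputs.** The plan does not fix their number, so a range is needed. Section 5.2.2.2 names 3 OBT measures. Section 12.3 item 6 lists 27 routine analytes or panels (lipid and thyroid counted as one each) and 6 optional assays: 3 + 27 + 6 = 36. The simulations take 35 as a rounded upper end.

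**3. Pure noise, criterion read on training data.** Independent Gaussian inputs, 50 v 150, near-unpenalised logistic regression (1000 runs per setting), or a network with one hidden layer of 3 units and weight decay 1e-4 (300 runs). The cut-off is the highest threshold with training sensitivity of at least 90%. All three targets means AUC ≥ 0.75 and specificity ≥ 50% at that cut-off.

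| Model | AUC ≥ 0.75 | All three targets |
|---|---|---|
| Logistic, 6 inputs | 0% | 0% |
| Logistic, 10 inputs | 0.2% | 0% |
| Logistic, 20 inputs | 10% | 1% |
| Logistic, best 6 of 35 | 4% | 1% |
| Logistic, all 35 | 79% | 28% |
| Network, 3 inputs | 9% | 2% |
| Network, 6 inputs | 79% | 26% |

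Nested 5-fold cross-validation gave a mean AUC of 0.49 to 0.50 and no passes in any of these settings.

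Other splits, AUC criterion (all three in brackets):
- 100 v 100: all 35 logistic 41% (5%); network with 6 inputs 55% (9%).
- 100 v 300: all 35 logistic 1% (0%); network with 6 inputs 7% (0.3%).
- 50 v 50, if only the two guaranteed minimum groups were contrasted (an assumption): logistic with 20 inputs 59% (21%); all 35, 100% (83%).

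**4. A weak real signal.** One predictor with true AUC 0.70 plus noise inputs, logistic, 50 v 150, 10-fold cross-validation, 300 runs:

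| Inputs | Training AUC | Cross-validated | New patients | Pass, training | Pass, cross-validated |
|---|---|---|---|---|---|
| 5 | 0.72 | 0.68 | 0.68 | 23% | 9% |
| 10 | 0.74 | 0.66 | 0.66 | 41% | 4% |
| 20 | 0.78 | 0.64 | 0.64 | 84% | 2% |
| 30 | 0.82 | 0.62 | 0.62 | 96% | 1% |

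Cross-validation tracks new-patient performance; the training AUC does not. With a predictor of true AUC 0.65, training against new-patient AUC was 0.68 v 0.62 with 6 inputs (3% pass), 0.74 v 0.59 with the best 6 of 35 (33% pass) and 0.81 v 0.57 with all 35 (96% pass).

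**5. Exact intervals.** With one real predictor of AUC 0.75 at 50 v 150, the nominal 95% exact interval for sensitivity covered new-patient sensitivity in 93% of runs with 6 inputs, 69% with the best 6 of 35 and 7% with all 35.

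**The case against.** The study is exploratory and for training, its performance analyses are called descriptive (section 11.7.1), and external validation is planned without condition. No decision in the documents hangs on the 0.75 bar; section 11.7.8.2 contains only a safety stop. This stands and limits the harm. It does not settle how a stated minimal criterion for sufficient efficacy is to be judged in this study.

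Cross-validation produces out-of-fold performance, and its sentence closes the paragraph that sets the targets, so the sponsor may intend the right reading. That is possible, but the text does not require it. A training AUC of 0.80 beside a cross-validated 0.60 would still pass.

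The largest figures come from extremes. The model sentence in section 11.7.5 names only OBT with or without MBT; section 7 speaks of one selected breath-test variable; laboratory inputs are optional. Correlation between inputs also matters: in one check with seven blocks of five correlated noise inputs (assumed correlation 0.5 to 0.7), the pass rate for the best 6 of 35 fell from 2.6% to 0.2%. For the 6-input network, the rate was 71% at weight decay 1e-4, 32% at 0.01 and 1% at 0.02. These points stand. The all-35, 50 v 50 and lightly penalised network results mark the upper end of what the plan permits, not what is likely.

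**Conclusion.** The concern holds. Nothing in the documents makes the AUC criterion or the sensitivity and specificity targets out-of-sample, and the open choice of inputs and method lets the training-data bias decide the result.

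The size depends on the number of inputs and the true signal, which the documents do not give. For a logistic model with about 10 or fewer prespecified inputs at 50 v 150, noise alone almost never passes (0.2% or less). A weak real signal can still pass too often: 41% on training data against 4% under cross-validation at 10 inputs, where new-patient AUC is 0.66. With wide input sets or lightly penalised networks the criterion carries little information.

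The consequence is a possibly wrong efficacy conclusion here and an optimistic cut-off taken forward, not direct harm to patients. It should be fixed but does not block the study.

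**What to change.** In section 11.7.5, state that the AUC criterion and the sensitivity and specificity targets are judged on cross-validated (or bootstrap optimism-corrected) predictions. Input selection, choice of model family, tuning and cut-off selection should be repeated within each training fold. Report training-set values and their exact intervals as descriptive only, and give intervals for the corrected values from a bootstrap of the whole process. Put matching wording in the synopsis under Data Analysis / Statistics.

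Stating the cut-off rule in advance, with some margin, is a useful addition: when the cut-off was set at exactly 90% training sensitivity, cross-validated sensitivity averaged 85% in the example below.

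The cost is wording and computing time, with no extra patients or data. Reported figures will be less favourable, and some good algorithms will miss the bar. With one real predictor of AUC 0.80 and 6 logistic inputs at 50 v 150 (new-patient AUC 0.79), the AUC criterion passes in 81% of runs under cross-validation against 97% on training data.

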5 BACKGROUND

Liver diseases can be caused by a variety of etiologies such as viral infection, metabolic diseases, alcohol abuse and autoimmune disorders. Liver disease can be acute or develop into chronic conditions. The conditions may vary from subtle disease to life threatening episodes, and/or may appear as mild inflammation up to significant inflammation leading to fibrosis, resulting in cirrhosis. Chronic liver disease and cirrhosis are currently the 12th leading cause of death, accounting for approximately 27,000 deaths annually (in the United States), increasing in numbers due to HCV, obesity and metabolic syndrome epidemic⁽¹⁾.

Standard biochemical and clinical tests are not capable of providing good correlation with disease staging and grading.

The unmet clinical need for a non-invasive means to evaluate liver fibrosis can be clearly reflected from the recently published NIH action plan for improving liver disease management. It positions this challenge second to improving HCV eradication rates.

The concept of a metabolic test, which could be utilized to assess the severity of liver disease, was first explored several decades ago. Such tests are performed by administering a compound either orally or intravenously, the compound is taken up by the liver and metabolized; the end-products of the metabolic process can be measured in either blood, bile, urine, saliva or exhaled breath, supplying a measurable value to the level of liver metabolic pathway. Several compounds have been utilized to evaluate hepatic metabolic function in this manner, including indocyanine green, galactose, aminopyrine, caffeine, lidocaine, phenylalanine, Methacetin and Octanoate [N-(4-Methoxy-phenyl) acetamide] and sodium-octanoate. For example, previous studies have demonstrated hepatic metabolism of lidocaine to monoethylglycinexylidide (MEGX) declines in association with liver fibrosis and cirrhosis and improves with successful treatment of the underlying liver disease. Furthermore, these studies showed the lidocaine test to accurately predict which patients with stable cirrhosis awaiting liver transplantation were at risk to develop future hepatic decompensation. Most of these methods have been abandoned due to impracticality or undesired side effects.

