6 INTENDED USE / INDICATION FOR USE

The BreathID[®] System together with ¹³C-Octanoate Breath Test (OBT) with or without ¹³C-Methacetin Breath Test (MBT) with or without additional clinical and/or laboratory parameters are to be used for the characterization of the histological image of Non-Alcoholic Fatty Liver Disease (NAFLD).

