8 STUDY DESIGN

This study is a multicenter, non-randomized, open-label, cross-sectional comparative exploratory study comparing OBT values with or without MBT values to histologic findings of liver biopsy.

This study will be used to train an algorithm using OBT with or without MBT combined with other commercially available biomarkers and to select a cut-off to correlate with histological findings, as assessed by a central reader, of NAFLD and determine clinical outcome at 18 and 36 months, if available.

The modeled algorithm will be validated in a separate study.

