9 STUDY OBJECTIVES

9.1 Efficacy Objective

The primary objective of the study is to develop an algorithm based on OBT with or without MBT with or without additional clinical and/or laboratory parameters, and its cut-off to correlate with histological findings, as assessed by a central reader, of NAFLD.

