11.2 Primary endpoints

Correlation of histological findings of NAFLD compared to ¹³C-Octanoate Breath Test with or without ¹³C-Methacetin Breath Test with or without additional clinical and/or laboratory parameters.

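### The AUC criterion of 0.75 is not tied to a named model and has no breath-free comparator, so if applied to the combined algorithm it cannot show what the breath test contributes

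*Combined protocol and SAP*

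**What the plan says.** Section 11.7.5 (Performance Analysis) states "The minimal criterion for sufficient efficacy is an Area under the Receiver Operating Characteristics (ROC) Curve (AUC", and the threshold it sets is "Area under the Receiver Operating Characteristics (ROC) Curve (AUC) ≥ 0.75 in this patient population". It adds targets for the cut-point: sensitivity of at least 90% and specificity of at least 50%. The model sentence in that section mentions OBT and optional MBT. It neither lists nor excludes other inputs.

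Other sections are wider:

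- Section 9.1: the aim is to "develop an algorithm based on OBT with or without MBT with or without additional clinical and/or laboratory parameters, and its cut-off".
- Section 11.2: the primary endpoint applies "with or without additional clinical and/or laboratory parameters". Section 9.4.1 gives the same scope.
- Section 8: the study is to "train an algorithm using OBT with or without MBT combined with other commercially available biomarkers".
- Section 6: the intended use is the breath test system "with or without additional clinical and/or laboratory parameters are to be used for the characterization of the histological image" of NAFLD.
- Section 11.6: the primary analysis set requires valid biopsy, OBT and MBT results together with the additional biomarkers.

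The rationale in Section 5 is that "Standard biochemical and clinical tests are not capable of providing good correlation with disease staging and grading". No AUC is given for those tests.

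**The concern.** The investigational product is the breath test system. An absolute AUC for an algorithm that may also contain blood tests measures the total discrimination of all inputs. It does not show how much comes from the breath test.

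Section 12.3 collects AST, ALT, platelets, insulin and glucose, and lipids and HbA1c, drawn afresh or taken from recent results. CK18, adiponectin and some other assays are optional. None of the planned checks measures added value:

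- Sections 11.5 and 11.7.6 look for confounding factors.
- Section 11.7.7 looks at centre effects.
- Cross-validation in Section 11.7.5 serves to test stability.
- The separate validation study (Sections 8 and 11.1) takes forward the algorithm as modelled.

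At stake is the choice of inputs. The training study is where a component that contributes little should be found. That applies to the breath test as a whole, and to MBT, which needs a second fasting visit at least 48 hours after OBT (Section 12.4). Otherwise the component is carried into the validation study.

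**Working it through.** **1. The plan's own figure.** Section 11.5 gives an AUC of 0.75 with a 95% half-width of 0.1, and class minimums of 50 NASH and 50 NAFLD. The Hanley-McNeil variance is [A(1−A) + (n1−1)(Q1−A²) + (n2−1)(Q2−A²)] / (n1·n2), with Q1 = A/(2−A) = 0.600 and Q2 = 2A²/(1+A) = 0.643. With 50 against 50, SE = 0.0488 and half-width = 1.96 × 0.0488 = 0.096. The Obuchowski binormal variance gives 0.102. The stated figure reproduces and is not in dispute.

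**2. Breath AUC needed for a combined AUC of 0.75.** Assumption: two independent, normally distributed, equal-variance scores, optimally combined. Then AUC = Φ(d/√2) and d² adds across the scores. An AUC of 0.75 gives d = 0.954, so breath d = √(0.954² − d_lab²). The clinical/laboratory AUCs are assumed, because the documents give none.

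| Clin/lab AUC | d_lab | Breath d needed | Breath AUC needed | Breath share of d² |
|---|---|---|---|---|
| 0.70 | 0.742 | 0.600 | 0.66 | 40% |
| 0.72 | 0.824 | 0.480 | 0.63 | 25% |
| 0.74 | 0.910 | 0.287 | 0.58 | 9% |
| 0.75 | 0.954 | 0 | 0.50 | 0% |

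Only the last two rows describe an algorithm whose discrimination comes almost wholly from non-breath inputs.

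**3. How often pure-noise breath variables would pass.** This is a simulation with 400 runs per setting: logistic regression, five routine markers with the joint AUC shown, three noise breath variables and 10-fold cross-validation. Each cell shows 50 against 150, then 100 against 100.

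| Assumed routine AUC | Apparent AUC ≥ 0.75 | Cross-validated AUC ≥ 0.75 |
|---|---|---|
| 0.70 | 35% / 24% | 5% / 4% |
| 0.75 | 76% / 75% | 25% / 22% |
| 0.80 | 97% / 98% | 71% / 80% |

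Models with breath variables only never reached 0.75. Section 11.7.5 does not say whether the apparent or the cross-validated AUC is judged.

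**4. Precision of a comparison.** SE of the difference = √(s1² + s2² − 2·r·s1·s2). Assumed: AUCs of 0.75 and 0.80, and a correlation r of 0.5 to 0.9 between the two estimates.

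| Classes | 95% half-width, r = 0.5 to 0.9 | Power for a 0.05 gain |
|---|---|---|
| 50 vs 50 | 0.092 to 0.042 | 19% to 65% |
| 50 vs 150 | 0.082 to 0.037 | 22% to 76% |
| 100 vs 100 | 0.065 to 0.029 | 33% to 92% |

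**5. Why the sign of the difference is not enough.** In simulations of the same kind (routine AUC 0.70 or 0.75, 500 runs per setting), adding three noise variables raised the apparent AUC in over 90% of runs. It raised the cross-validated AUC in fewer than 30%.

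**The case against.** The best counter-argument is textual. The section that holds the criterion speaks only of OBT and MBT, Section 7 speaks of training a variable based on those tests, and Section 11.7.6 speaks of their correlation with the biopsy diagnosis. If 0.75 applies to a breath-only score, blood tests cannot satisfy it. That reading is tenable, but so is the wider one, and nothing in the plan chooses between them. The ambiguity is itself part of the defect.

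Second, the study is exploratory, its performance analyses are descriptive (Section 11.7.1), the criterion is called minimal, and validation follows separately. This limits the consequence and caps the severity. It does not fill the gap, because the later study validates the same algorithm.

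Third, the synopsis uses ROC analysis to find the optimal parameter, so some comparison of OBT with OBT plus MBT is implied. What is missing is a paired estimate with an interval.

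Fourth, a comparison would be imprecise. That is true (step 4), and it argues for an estimate with its interval, not a powered test.

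Two stronger readings are tempting. A reader might infer that routine blood tests would meet the criterion while the breath test adds nothing. The documents do not support that. They give no AUC for routine tests, Section 5 asserts that such tests correlate poorly, and at an assumed routine AUC of 0.70 noise breath variables passed on cross-validated AUC in only 4% to 5% of runs. A reader might also infer that every candidate input is already in hand. Section 12.3 makes CK18, adiponectin and similar assays optional, and allows hepatic results up to 3 months old and lipid and HbA1c results up to 6 months old.

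**Conclusion.** The point holds in conditional form. The plan does not say which model the 0.75 criterion governs, and it contains no breath-free model or difference in AUC. If the combined algorithm is judged, passing does not show that the breath test contributes. The breath AUC needed falls from 0.66 to 0.50 as the clinical/laboratory AUC rises from 0.70 to 0.75. These figures rest on independent, equal-variance normal scores and on assumed clinical/laboratory AUCs. At 0.70 or 0.72 the breath test would still supply 40% or 25% of the squared separation, so the issue becomes serious only near or above 0.75. The plan never measures the quantity that decides this. For an exploratory training study, this is a change that should be made, and no stronger grade is warranted.

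**What to change.** In Section 11.7.5:

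1. State which model the 0.75 criterion governs: breath variables only, or the combined algorithm.
2. Fit a clinical/laboratory-only model alongside the final algorithm, on the same patients with complete data, by the same method and with the same cross-validation folds. Use the routinely collected parameters, and the optional assays only where available. Report the paired difference in cross-validated AUC with its 95% CI next to the 0.75 criterion.
3. Report OBT alone against OBT plus MBT in the same way.
4. Interpret both differences descriptively from the whole interval, not from their sign or from apparent AUC. If the interval for the difference in item 2 includes zero, do not attribute the algorithm's performance to the breath test. Given the width, such an interval would not prove that the breath test contributes nothing.

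The cost is SAP wording and a modest analysis, with no new patients or procedures. The drawbacks are an imprecise difference (half-width about 0.03 to 0.09 under the assumptions in step 4) and a headline that may look less favourable to the device.
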